19.1.2.4 Symptomatic Deterioration

Patients with a global deterioration of health status requiring discontinuation of treatment without objective evidence of disease progression at that time should be reported as ‘symptomatic deterioration’. Every effort should be made to document objective progression even after discontinuation of treatment. Symptomatic deterioration is not a descriptor of an objective response: it is a reason for stopping study therapy. The objective response status of such patients is to be determined by evaluation of target and non-target disease.

19.2 Appendix B: Cytochrome P-450 (CYP) interactions

A sample list of CYP450 inhibitors and inducers are provided. This list is not intended to be exhaustive, and the prescribing information of the concomitant medication should be consulted if the status is unclear. Additionally, a website such as www.drug-interaction.com could be consulted, if appropriate.

19.2.1 CYP3A4 Inhibitors

Source: Cytochrome P450 Drug Interaction Table ([Flockhart, 2007](#))

Amiodarone	Indinavir
Aprepitant	Itraconazole
Chloramphenicol	Ketoconazole
Cimetidine	Mibepradil
Ciprofloxacin	Mifepristone
Clarithromycin	Nefazodone
Delavirdine	Nelfinavir
Diethyldithiocarbamate	Norfloxacin
Diltiazem	Ritonavir
Erythromycin	Saquinavir
Fluconazole	Star fruit
Fluvoxamine	Telithromycin
Gestodene	Verapamil

Grapefruit juice

Voriconazole

Imatinib

19.2.2 CYP3A4 Inducers:

Source: Cytochrome P450 Drug Interaction Table ([Flockhart, 2007](#)).

(EIAED are marked with asterisks)

Barbiturates*	Phenobarbital*
Carbamazepine*	Phenytoin*
Efavirenz	Pioglitazone
Glucocorticoids	Primidone*
Modafinil	Rifabutin
Nevirapine	Rifampin
Oxcarbazepine	St. John's wort

19.3 Appendix C: Guidance for Managing Hyperglycemia

Hyperglycemia is a potential class effect of drugs inhibiting mTOR signaling pathways ([Sankhala, 2009](#)). Consequently, this protocol requires close monitoring and early intervention for hyperglycemia.

To detect meaningful incipient hyperglycemia, in Cycle 1 careful review of blood glucose results and possible hyperglycemic symptoms are need during the routine weekly clinic visits. Subjects must also be instructed how to contact study staff immediately in the event of symptoms (eg, polyuria, thirst), in which case prompt assessment in the clinic is necessary.

[figure not shown]
In the event of modest or intermittent hyperglycemia, more frequent monitoring may be required. In the event of persistent fasting hyperglycemia (> 126 mg/dL), or at any time considered appropriate by the Investigator, it is recommended that oral hypoglycemic therapy be initiated. Metformin hydrochloride 464 mg PO nocte is an appropriate starting therapy. It is recommended that dosage be increased by 464 mg every 3 days (or slower in the event of gastrointestinal or other intolerance) to a maximum of 2000 mg. Glucophage, and other biguanide therapy, should be temporarily suspended when planned radiological tumor assessments (e.g., CT scan) involve iodinated contrast (see Section [6.4.1](#)). Subjects should be instructed on how to recognize hypo- and hyperglycemia. Treatment interruptions of > 3 weeks will necessitate removal of the subject from this study.

[Goldberg, 2004](#); [Goldberg, 2005](#); and [Turina, 2006](#) are suggested resources for hyperglycemia management.

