5. TABLE OF EVENTS

Table 3: Table of Events

	Screening Period	Treatment Period							Follow-up Period	
		Cycle 1 (single dosing)		Cycle 1 (continuing dosing)		Cycle 2		Subsequent cycles		
Study Day ^a	-29 to -2 ^b	-1	0	1	15	1	15	1		Disease progression/survival
Study Entry										
Informed consent	X									
Prior cancer history	X									
Prior cancer therapies ^c	X									
Demographics	X									
Complete medical history	X									
Prior/ concomitant medication evaluation	X			Continuous, until 28 days after treatment discontinuation						
Prior/ concomitant procedures evaluation	X			Continuous, until 28 days after treatment discontinuation						
Inclusion/exclusion criteria	X									

Table 3: Table of events (continued)

	Screening Period	Treatment Period							Follow-up Period				
		Screening		Cycle 1 (single dosing)	Cycle 1 (continuing dosing)	Cycle 2		Subsequent cycles					
Study Day^a	-29 to -2^b	-1	0	1	15	1	15	1	Disease progression/survival				
Investigational Product													
Administer ATG-008		X		Daily, continuously									
Safety Assessment													
Adverse event collection	Continuous starting after informed consent signature, until 28 days after last dose of IP												
Weight	X			X		X		X	X				
Height	X												
Vital signs	X			X	X	X	X	X					
Hematology laboratory	X(-7 to -1)			X		X	X	X	X				
Coagulation function test	X(-7 to -1)					X		X					
Fasting chemistry laboratory test	X(-7 to -1)				X	X	X	X					
Special chemistry: Amylase, lipase, TSH, fT4	X(-7 to -1)					X		X					

Table 3: Table of events (continued)

	Screening Period	Treatment Period							Follow-up Period
		Cycle 1 (single dosing)		Cycle 1 (continuing dosing)		Cycle 2		Subsequent cycles	
Study Day^a	-29 to -2^b	-1	0	1	15	1	15	1	
HbA1c	X(-7 to -1)							Every other cycle starting in Cycle 3	
AFP	X					X		X	X
HBV and HCV serologies (HBsAg, HBeAg, HBsAb, HBeAb, HBcAb, HCVAb)	X								
HBV viral load ^d	X					X		X	
Urine routine	X(-7 to -1)				X	X	X	X	
12-lead electrocardiogram (local assessment)	X								X
Serum β-hCG (in FCBP)	X							As clinically indicated	
Urine β-hCG (FCBP)	X ^e (-72 hrs to 0 hr from dosing)					X		X	X
PK samples(blood) ^f		X	X	X	X				
PK samples (urine) ^g		X	X						

Table 3: Table of events (continued)

	Screening Period	Treatment Period							Follow-up Period
		Cycle 1 (single dosing)		Cycle 1 (continuing dosing)		Cycle 2		Subsequent cycles	
Study Day ^a	-29 to -2 ^b	-1	0	1	15	1	15	1	Disease progression/survival

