Efficacy Assessments									
Tumor assessments(CT/MRI, see Section 6.4)	X			Every 8 weeks (\pm 5 days) from enrollment (first dose), until radiologic progression					
ECOG performance status	X			X		X		X	X
Follow-up									
Survival follow-up									Every 8 weeks (\pm 1 week)
Anticancer therapy after treatment discontinuation									Every 8 weeks (\pm 1 week)

^a All visits have a \pm 3 day window, except Cycle 1 Day 1 (which must occur within 28 days of signing the ICF).

^b Screening assessments must be performed prior to study treatment, however these events may occur on the same calendar day as long as the chronological order is followed.

^c Prior cancer therapies includes surgery, radiation, systemic, locoregional or any other therapy (e.g. hormonal) for the subject's cancer.

^d HBV viral load is collected in subsequent cycles only in subjects with chronic HBV infection, positive HBeAg, positive HBcAb or positive viral load at screening.

^e Urine β -hCG (or local serum) at screening within 72 hours of Cycle 1 Day -1 dose.

^f PK samples (blood) should be taken at each scheduled day, according to the schedule in Section 6.5.1.

^g PK samples (urine) should be taken at each scheduled day, according to the schedule in Section 6.5.2.

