- Prior and concomitant medication evaluation (includes those taken ≤ 28 days before the screening visit, except those taken for cancer which are recorded as part of prior cancer therapy).
- Prior and concomitant procedures (includes all procedures occurring ≤ 28 days before the screening visit).
- Adverse event evaluation (begins when the subject signs the informed consent form [ICF]).
- Vital signs (including blood pressure, temperature and pulse).
- Hematology: Complete blood count (CBC) with differential, including red blood cell (RBC) count, hemoglobin, hematocrit, white blood cell (WBC) count with absolute differentials (neutrophils, lymphocytes, monocytes, eosinophils and

basophils), and platelet count; within 7 days of the first dose of study drug.

- Coagulation panel: Prothrombin time (PT), international normalized ratio (INR), partial thromboplastin time (PTT); within 7 days of the first dose of study drug.
- Fasting chemistry laboratory: Includes sodium, potassium, chloride, calcium, magnesium, phosphorus, glucose, blood urea nitrogen (BUN), creatinine, albumin, total protein, alkaline phosphatase, bilirubin (total and direct), aspartate amino transferase (AST/SGOT), alanine amino transferase (ALT/SGPT), lactate dehydrogenase (LDH), uric acid, cholesterol and triglycerides; within 7 days of the first dose of study drug.
- Special chemistry laboratory: Amylase, lipase, thyroid stimulating hormone (TSH), free T4 (fT4); within 7 days of the first dose of study drug.
- Hemoglobin A1c (HbA1c) within 7 days of the first dose of study drug.
- AFP.
- Hepatitis B virus (HBV) and hepatitis C virus (HCV) serologies (hepatitis B surface antigen [HBsAg], hepatitis B e antigen [HBeAg], hepatitis B surface antibody [HBsAb], hepatitis B e antibody [HBeAb], hepatitis B core antibody [HBcAb], hepatitis C virus antibody [HCVAb]).
- HBV viral load.
- Urine routine within 7 days of the first dose of study drug.
- 12-lead electrocardiogram (ECG), single local assessment; when an ECG time-point coincides with any other assessment, the ECG should always be collected first.
- Pregnancy test (β -hCG) is required for all female subjects of child-bearing potential. Serum β -hCG pregnancy test will be performed at screening. A urine (or local serum) pregnancy test will be performed to assess subject eligibility within 72 hours prior to the first administration of study drug.

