6.2. Treatment Period

After signed the ICF within 28 days, the eligible subjects must start treatment as soon as possible. For all subsequent visits, an administrative window of \pm 3 days is permitted, otherwise specified.

Subjects will receive a single dose of ATG-008 on Day -1, followed by a 48-hour observation for PK sample collection.

- Oral daily dosing of 15 mg or 30 mg begin on Day 1 and will continue in 28-day cycles
- It is planned that approximately 20 subjects will receive oral ATG-008 at an initial dose of 45 mg/QD and another 20 subjects will receive oral ATG-008 at an initial dose of 20 mg/BID. The 28 continuous days are regarded as one treatment cycle. The pharmacokinetic (PK) samples will be collected from 10 subjects each in the two dose groups.

The subjects will continue to use ATG-008 until radiologic disease progression, intolerable toxicities, or withdrawal of consent for further dosing (in which case subjects will continue to be followed for further anticancer treatment and survival status unless consent for this has been explicitly withdrawn). Subjects will fast ≥ 6 hours before those clinical visits which require evaluation of PK and fasting chemistry examination. PK, safety and tolerability for the 30-mg dose level will follow the assessment of the 15-mg dose level if DLTs occur in less than 2 of 6 subjects at the 15-mg dose level who complete Cycle 1.

The following evaluations will be performed at the frequency specified in the Table of Events, [Table 3](#). The evaluations should be performed prior to dosing on the visit day, unless otherwise specified.

- Adverse event evaluation (continuously)
- Concomitant medications evaluation (including medications for best supportive care)
- Concomitant procedures evaluation
- ECOG performance status
- Vital signs, weight
- Hematology laboratory
- Coagulation panel
- Fasting chemistry laboratory
- Special chemistry laboratory
- HbA1c
- Urine routine
- AFP
- HBV viral load (in subjects with positive HBsAg, HBeAg HBcAb or positive viral load at screening).
- Urine β -hCG (females of childbearing potential (FCBP) only)
- Radiologic response assessment/tumor evaluation and assessment of disease progression (see Section 6.4)

- PK sampling (see Section 6.5)

Detailed evaluations are listed in [Table 3](#).

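### Appendix C relies on weekly Cycle 1 visits for glucose and symptom review, but Table 3, which sets the visit schedule, has no Day 8 or Day 22 visit

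*Combined protocol and SAP*

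**What the plan says.** Appendix C treats hyperglycemia as a possible class effect and states that "this protocol requires close monitoring and early intervention for hyperglycemia". To catch it early in Cycle 1, it relies on review of glucose results and symptoms "during the routine weekly clinic visits".

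The schedule is set elsewhere. Section 6.2 states: "The following evaluations will be performed at the frequency specified in the Table of Events". In Table 3 (Section 5), the Study Day header lists Days -1 and 0 for the single-dose part of Cycle 1, Days 1 and 15 for the daily-dosing part, and then Cycle 2 Day 1. The same header repeats in each continued part of the table.

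Glucose is measured in the fasting chemistry panel. Section 6.1 defines it: "Fasting chemistry laboratory: Includes sodium, potassium, chloride, calcium, magnesium, phosphorus, glucose". The Table 3 row "Fasting chemistry laboratory test" is marked at screening (Day -7 to -1), Cycle 1 Day 15, Cycle 2 Days 1 and 15, and subsequent cycles. The synopsis names fasting plasma glucose as a monitored test but gives no frequency. On treatment, HbA1c is scheduled only from Cycle 3.

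Table 4 (Section 8.2.1.2) sends sites to Appendix C for Grade 3 or 4 hyperglycemia and allows 7 days of medical management before a dose reduction.

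**The concern.** Appendix C depends on visits that the controlling schedule does not contain. In a subject without symptoms, management can begin only once glucose has been measured. That applies to oral therapy for persistent fasting hyperglycemia, to metformin titration and to the 7-day period in Table 4. If sites work from Table 3, the first scheduled on-treatment glucose result comes in the third week of daily dosing.

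The timing matters. This version of the protocol opens groups at 45 mg and 40 mg per day. In this study's own data at 15 and 30 mg, hyperglycemia was the most frequent drug-related event of Grade 3 or above, at 24.2% (Section 1.3.2.4).

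**Working it through.** The protocol states no figure to reproduce. The check compares two schedules.

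**Weekly points.** Daily dosing starts on Day 1 and runs in 28-day cycles (Section 6.2). Weekly points after that start are 1 + 7 = 8, 8 + 7 = 15 and 15 + 7 = 22. Table 3 has Day 15 only, so 1 of 3. If Day 1 is counted as a weekly visit, 2 of 4 visits exist (Days 1 and 15), but glucose is marked at only 1 of the 4.

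**Can the visit window close the gap?** Table 3, footnote a, allows 3 days either side, with an exception: "day window, except Cycle 1 Day 1 (which must occur within 28 days of signing the ICF". Day 15 covers 15 - 3 = 12 to 15 + 3 = 18. Cycle 2 Day 1 is taken as Day 29, assuming 28 days of daily dosing from Day 1, and reaches back to 29 - 3 = 26. Neither window includes Day 8 or Day 22.

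**Gap before the first on-treatment glucose check.**
- As the row is marked: from Day -1, 15 - (-1) = 16 days; from Day -7, 15 - (-7) = 22 days. The nominal gap is 16 to 22 days.
- If a Day 1 mark was lost in PDF reading: 15 - 1 = 14 days, or 12 - 1 = 11 to 18 - 1 = 17 with the Day 15 window.

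A Day 1 sample would not restore weekly review. Section 6.2 says "Subjects will receive a single dose of ATG-008 on Day -1, followed by a 48-hour observation for PK sample collection", and also "The evaluations should be performed prior to dosing on the visit day". A Day 1 sample would therefore reflect one dose and precede the first daily dose.

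**Gap to the next check.** Day 15 to Day 29 is 14 days. With both windows it runs from 26 - 18 = 8 to 32 - 12 = 20 days.

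**What is known about frequency.**
- Drug-related hyperglycemia of Grade 3 or above: 24.2% of 33 is 8 subjects; 8/33 has an exact (Clopper-Pearson) 95% CI of 11.1% to 42.3%. This covers any time on treatment, with an average of 3.2 cycles. It is not a Cycle 1 rate.
- Dose-limiting toxicities: one at 15 mg and none at 30 mg, in 7 + 28 = 35 subjects (Section 4.2). Section 4.1 counts hyperglycemia of Grade 3 or above as a DLT. If that definition was applied to all 35 over Cycle 1, at most 1/35 (2.9%, exact 95% CI 0.1% to 14.9%) had a recognised Cycle 1 event. The Cycle 1 period is inferred from the escalation rule, and one subject was still in Cycle 1 at that cutoff.

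These two results suggest that few Grade 3 or higher events were recognised in Cycle 1 at the lower doses. They cannot show whether few occurred or whether sparse testing missed some.

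**The case against.** The strongest reply is that Appendix C is itself part of the plan. It is the more specific text on this risk, and Table 4 points to it. A site that follows it would review glucose weekly, so a reader should not infer that every subject gets only one of three checks. That stands. The supported statement is that the two parts disagree and that a site working from Table 3 falls short. The reply confirms the disagreement and does not resolve it, because Section 6.2 gives frequency to Table 3 and Table 3 has no such visits.

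A figure in Appendix C is not shown in the available text and may bear on glucose management. That limits what can be said about the appendix as a whole. It does not add Day 8 or Day 22 columns to Table 3.

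Safeguards also remain: subjects are told to contact staff about symptoms and are then assessed promptly, monitoring may be stepped up once glucose is raised, the investigator may start therapy whenever judged appropriate, HbA1c above 7% is an exclusion, and adverse events are collected continuously. These reduce the risk. Apart from the HbA1c exclusion at entry and the investigator's discretion, they act mainly after symptoms or a known raised glucose, whereas the weekly review is meant to find early cases.

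A reader might also infer that about a quarter of the new subjects would have severe hyperglycemia go unseen in Cycle 1. The documents do not support this: the 24.2% is an any-time rate at lower doses, the DLT count points to few recognised Cycle 1 events, and no onset times are given.

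Finally, rewording Appendix C to a two-weekly schedule would also remove the inconsistency. It would, but it gives up the early detection that the appendix calls for.

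**Conclusion.** Wrong as written: an internal inconsistency that affects safety monitoring. A site following Table 3 covers 1 of 3 weekly points after daily dosing starts, with a nominal 16 to 22 days between the screening glucose and the first on-treatment one, and about 14 days to the next.

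The visit count rests on the repeated Study Day header and is firm. The 16-to-22-day gap rests on the fasting chemistry row having no Day 1 mark. The second interval assumes that Cycle 2 Day 1 falls on Day 29.

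The size of any harm is not established, and no projection to the next 40 subjects is justified. The sponsor should still correct this before the higher daily doses start, because the toxicity is frequent at lower doses and the correction is small.

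**What to change.** Before the 45 mg once-daily and 20 mg twice-daily groups are dosed, amend Table 3 to add a local fasting glucose check with symptom review at about Cycle 1 Days 8 and 22. In the same amendment, state whether fasting chemistry is intended on Day 1.

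The cost is two short local checks per subject: 2 x 40 = 80 for the planned 40 subjects, and up to 2 x (40 + 110) = 300 if the expansion of about 110 goes ahead. Appendix C already presumes these visits, so the amendment brings the schedule into line with it.

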19.4 Appendix D: Liver Cancer Staging, and Child-Pugh Classification

19.4.1 Barcelona Clinic Liver Center Staging

Figure 2: Barcelona-Clinic Liver staging classification and treatment schedule

BCLC = Barcelona-Clinic Liver staging classification and treatment schedule.

Note: From Pons, 2005 adapted from [Llovet, 2003](#).

19.4.2 Child-Pugh Classification of Liver Failure

Subjects with Child-Pugh A and B7 and hepatic encephalopathy scored as 1 point meet this individual inclusion criterion for the study.

Table 7: Child-Pugh Classification

	1 point	2 points	3 points
Bilirubin (mg/dL)	< 2	2-3	> 3
Albumin (g/L)	> 3.5	2.8-3.5	< 2.8
Prothrombin time prolonged in seconds (INR)	1-4 (< 1.7)	4-6 (1.7-2.3)	> 6 (> 2.3)
Ascites	None	Slight	Moderate
Hepatic encephalopathy	None	Grade 1-2	Grade 3-4
Child A: 5-6 points; Child B: 7-9 points; Child C: ≥ 10 points			

Source: [Pugh, 1973](#)
